8.4 Premature Termination and Handling of Missing Data

Any premature termination of the study therapy will be recorded in CRF. Listing of the subjects with premature termination will be provided with the dates and reasons. Missing data caused by premature termination will be utilized the last observation carried forward (LOCF).

9. Quality Control and Quality Assurance

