6.6 Analysis of Efficacy

6.6.1 Primary Efficacy Endpoint

An improvement of 40% or greater response rate from baseline in treatment group is considered effective and worth further study. The endpoint will be analyzed by checking if the difference of counts of responder is larger than 0 between PDC-1421 arm and placebo arm. Missing data caused by premature termination will be utilized the last observation carried forward (LOCF).

The response rate in the ADHD-RS-IV total score is defined as the following formula.

$$\text{Response rate} = \frac{\text{score}_{\text{visit}} - \text{score}_{\text{baseline}}}{\text{score}_{\text{baseline}}}$$

and the responder is defined as

$$\text{Responder : response rate} \geq 40\%$$

The descriptive statistics will include the proportion of subjects who achieved at least 40% improvement of the ADHD-RS-IV total score at Visit 6 by treatment group and placebo group. The frequency distribution of pre-treatment and post-treatment will also be tabulate and report in bar graph.

The primary measure of efficacy was the ADHD-RS-IV, consisting of 18 items designed to reflect current symptomatology of ADHD based on DSM-IV-TR criteria. Each item is scored on a 4-point scale ranging from 0 (reflecting no symptoms) to 3 (reflecting sever symptoms) with total scores ranging from 0 to 54, which is calculated by summing up scores of subscales. The 18 items may be grouped into 2 subscales:

- For inattention (IA) subscale raw score: Add the odd-numbered 9 items. Higher score indicate severe inattention symptoms.
- For hyperactivity-impulsivity (HI) subscale raw score: Add the even-numbered 9 items. Higher score indicate severe hyperactivity-impulsivity symptoms.
- To obtain the total raw score: Add the IA and HI subscale raw scores.

Following SAS procedures will be applied for chi-Square test between arms.

```
%macro;  
proc freq data = ____;  
    table response*treatment/chisq;  
    output out = chiqtest chisq;  
run;  
%mend;
```

When there has a missing value issue, the following LOCF SAS procedures will be applied.

```
%macro;  
DTAT locf1;  
    LENGTH dtype $15;  
    RETAIN retain;  
    SET lab;  
    BY usubjid visit;  
  
    IF FIRST . visit ^=0 THEN retain = . ;  
    IF qsstresc NE . THEN retain = qsstresc;  
    IF qsstresc= . THEN DO;  
        qsstresclocf = retain;  
        dtype = 'LOCF';  
    END;  
    ELSE qsstresclocf = qsstresc;  
RUN;  
%mend;
```

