6.8 Statistical / Analytical Issues

6.8.1 Handling of Dropouts or Missing Data

The data are analyzed utilizing the last observation carried forward (LOCF) technique to impute the missing data.

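### The LOCF program printed in SAP 6.6.1 cannot carry a score from one visit to the next, so it contradicts the LOCF rule stated in the SAP and the protocol

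*SAP*

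**What the plan says.** The rule in words is consistent. Protocol 8.4: "Missing data caused by premature termination will be utilized the last observation carried forward (LOCF". Protocol 8.3 says the same for the analysis in general, SAP 6.6.1 repeats it for the primary endpoint, and SAP 6.8.1 has "The data are analyzed utilizing the last observation carried forward (LOCF) technique to impute the missing data".

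SAP 6.6.1 then gives code and states its role: "When there has a missing value issue, the following LOCF SAS procedures will be applied". The lines that matter are, in order:

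- the grouping, "BY usubjid visit";
- the reset of the carried value to missing, beginning "IF FIRST . visit ^=0 THEN retain";
- the update when a score is present, "IF qsstresc NE . THEN retain = qsstresc";
- the imputation when the score is missing, "qsstresclocf = retain", with `dtype` set to 'LOCF' on that record.

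The result feeds the primary summary, which is the proportion with "at least 40% improvement of the ADHD-RS-IV total score at Visit 6". SAP 6.2 draws the primary conclusion from the ITT population. SAP 5.3.1 does not require a Visit 6 score for ITT membership, so a subject who stops early can be in it.

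**The concern.** LOCF needs the carried value to survive from one visit to the next within a subject and to be cleared only when a new subject (or a new parameter) begins. The printed step clears it whenever a new visit begins. The section's text and its code therefore give different Visit 6 values for the same subject.

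At stake is the ITT responder count and proportion at Visit 6. SAP 5.4 cancels the between-arm tests because the study was terminated, but these descriptive results remain. The per-protocol set offers no check, because SAP 5.3.1 restricts it to subjects with complete primary-endpoint data. The label adds a difficulty: a record that received no value still carries the LOCF flag, so counting flags would suggest that imputation had been done.

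**Working it through.** The plan gives no figure on this point to reproduce. The design's operating characteristics do not enter the argument. They do reproduce: exact enumeration for one active arm against placebo gives alpha 0.139 and power 0.801, against the stated 0.15 and 80%.

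**Step 1: logic of the reset.** Under a BY statement with subject then visit, `FIRST.visit` equals 1 on the first record of each subject-visit combination, including when the subject changes. With one total score per visit, that is every record. On a record with a missing score the order is: clear the carried value, skip the update, assign the carried value. The assigned value is therefore missing.

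**Step 2: one record per visit.** Illustrative subject, with the step followed record by record:

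| | Visit 2 (baseline) | Visit 3 | Visit 4 | Visit 5 | Visit 6 |
|---|---|---|---|---|---|
| Observed | 40 | 30 | 22 | missing | missing |
| Printed step | 40 | 30 | 22 | missing, flagged LOCF | missing, flagged LOCF |
| Reset once per subject | 40 | 30 | 22 | 22, flagged LOCF | 22, flagged LOCF |

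Change at Visit 6 under true LOCF: (22 − 40)/40 = −0.45. The SAP formula is visit minus baseline, so an improvement comes out negative. Read as a 45% reduction, it exceeds 40% and the subject is a responder. Under the printed step there is no Visit 6 value and no response can be recorded.

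Intermittent gaps behave the same way. With 40, 30, missing, 22, 20 at Visits 2 to 6, Visit 4 stays missing under the printed step and becomes 30 under a per-subject reset.

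**Step 3: several records per visit.** Suppose the dataset holds items. At Visit 5, item a = 1 and item b is missing; at Visit 6 both are missing. The printed step gives item b at Visit 5 the value 1, taken from item a, and leaves both Visit 6 items missing. It carries between rows of the same visit and never across visits. A reset on subject alone would fill both Visit 6 items with 1, also from item a, which is why the parameter must be in the key when several are held.

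**Step 4: absent rows.** The step creates no records. If a subject has rows only up to Visit 4, even a per-subject reset yields nothing at Visit 6. The documents do not describe the dataset, so this is a condition to verify.

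**Step 5: size.** The documents give no dropout rate. As an assumption only, 15% to 20% of the 23 per arm in Stage I is 0.15 × 23 = 3.45 to 0.20 × 23 = 4.6, or roughly 3 to 5 subjects. Only those whose last observed score already meets the 40% criterion change status. If that share were 20% to 40% (a further assumption, borrowed from the design's response rates), the loss would be 3 × 0.20 = 0.6 to 5 × 0.40 = 2.0 responders per arm, partly cancelling in the difference from placebo.

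**The case against.** The strongest reply is that the printed block is a template and that the text governs. The companion frequency step has a blank dataset name, the macro has no name, and `DTAT` would not execute. The rule is stated in words in four places, so a competent programmer would have implemented LOCF correctly. The input name `lab` also looks like a leftover, since the variable read is `qsstresc`. Much of this is fair. Some of the oddities may come from PDF reading, and the point does not use them. But repairing the typography does not cure the reset, and the SAP says this is what will be applied.

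Timing also limits the point. The SAP was approved on April 25, 2024 and already records the termination. The LOCF flag on empty records would also be visible in a listing, so the failure is misleading but not hidden.

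A reader might infer more than the documents support:

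- *That the primary endpoint was in fact missing for every dropout, or that the code drove the interim result and the termination.* Nothing shows which program was run.
- *That the final cut-off of 4 responders is affected.* That cut-off applies to counts accumulated after Stage II, and SAP 5.4 says the study was terminated on the interim results.
- *That each dropout shifts the responder difference by 1.* Only a subject whose last score meets the 40% criterion does so.
- *That a carried pre-dose score would distort the primary count.* Carrying the baseline itself gives 0% change, a non-responder.

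Whether LOCF should be confined to efficacy scales is a separate choice and not part of this defect.

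**Conclusion.** The point holds as a conflict between code and text. Under either data layout, the printed step carries no score across visits, whereas SAP 6.6.1, SAP 6.8.1 and Protocol 8.3 and 8.4 all call for LOCF. If it was run as printed, ITT subjects without a Visit 6 score whose last ADHD-RS-IV total showed at least 40% improvement were left out of the responder count. Whether they stay in the denominator of the proportion is not stated.

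The number affected is unknown. The range of 0.6 to 2.0 responders per arm rests on an assumed dropout rate and an assumed share of responders among dropouts, and shows scale only. The conclusion about the code needs no such assumption, because it follows from the BY variables and the reset condition.

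**What to change.** Correct the printed step:

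1. Make sure a row exists for every scheduled visit before imputation.
2. Sort by subject and visit and reset on `FIRST.usubjid`. If the dataset holds several parameters, sort by subject, parameter and visit and reset on `FIRST.paramcd`.
3. Read the rating-scale dataset in place of `lab`.

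Then confirm in writing which code produced the Visit 6 ITT responder counts and proportions, including the interim table. If it used the printed logic, re-run those tables with the corrected step and report any subject whose status changes. If it did not, record that the printed block was unused and replace it with the code that was run.

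The cost is a few lines of code and, at most, one re-run. The stated missing-data rule is unchanged.

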6.6.2 Secondary Efficacy Endpoints

- **ADHD-RS-IV**

The scores of ADHD-RS-IV will be assessed by the descriptive statistics.

- **CGI**

The scores of 2 or lower of CGI will be summarized by way of frequency and percentage.

At the screen and baseline visit, clinicians completed the CGI-S and were asked to evaluate the severity of subjects' illness with respect to ADHD symptoms based on the clinician's experience with this particular population. Possible scores ranged from 1 (normal, not ill at all) to 7 (among the most extremely ill subjects). At all subsequent study visits, clinicians used the CGI-I to rate the subjects' total improvement based on comparison with their baseline assessment from 1 (very much improved) to 7 (very much worse).

- **CAARS-S:S**

The T-scores of CAARS-S:S (Conners et al. 1999) will be assessed for each visit change from baseline by the descriptive statistics

Conners' Adult Attention-Deficit/Hyperactivity Disorder Rating Scale-Self Report: Short Version (Conners et al., 1998; CAARS-S:S) consists of 26 items rated from 0 'not at all, never' to 3 'very much, very frequently.' Four subscales each composed of 5 items (A: Inattention/Memory Problems; B:

Hyperactivity/Restlessness; C: Impulsivity/Emotional Lability; and D: Problems with Self-Concept) as well as a 12-item ADHD index can be computed. The raw scores were converted into standard T-scores by Microsoft Excel program which designed according to the Profile form of CAARS QuikScore forms. A T-score is a standard score with a mean of 50 and a standard deviation of 10 in all samples and across all scales. As a general guide, T-scores can be interpreted using the guidelines provided in the table below. The CAARS-S:S was self-assessed by the subjects from Visit 1 to Visit 7.

Interpretive Guidelines for T-Scores and Percentiles

T-Score Range	Percentile Range	Guideline
Above 70	98+	Very much above average
66 to 70	94 - 98	Much above average
61 to 65	86 - 94	Above average
56 to 60	74 - 85	Slightly above average
45 to 55	27 - 73	Average
40 to 44	16 - 26	Slightly below average
35 to 39	6 - 15	Below average
30 to 34	2 - 5	Much below average
Below 30	< 2	Very much below average

Reference: CAARS Adult ADHD Rating Scales Technical Manual

• E-SCT

The scores of E-SCT will be assessed for each visit change from baseline by the descriptive statistics

The E-SCT rating scale queries 15 Sluggish Cognitive Tempo symptoms rated from 0 = Never or Rarely, 1 = Sometimes, 2 = Often, 3 = Very Often, grouped into latent factors of daydreaming, working memory problems, and subjective sleepiness/tiredness. The scale was empirically derived from a set of 44 candidate items 17. Sluggish Cognitive Tempo has been shown to be a statistically related but distinct syndrome with respect to ADHD 18. The range for the Total Score is 0-45. Factor scores are computed using this same method. For data analysis, mean item scores will be used to protect against missing data.

6.7 Analysis of Safety

6.7.1 Adverse events (AEs)

The coding system used will be the Medical Dictionary for Regulatory Activities (MedDRA).

Pre-treatment AE is the AE onset before the first dosing of study drug, while treatment-emergent AE is the one onset after the first dosing of study drug. Pre-treatment AE and treatment emergent AE will be analyzed separately.

Frequency table of subjects with pre-treatment AE (PTAE) and treatment emergent AE (TEAE) will be presented by center and treatment.

For TEAE, adverse event incidents will also be summarized descriptively by system organ class and preferred term using MedDRA. If more than one type of event occurred within a system organ class/ preferred term for the

subject, the subject is counted only once for each system organ class/ preferred term.

For TEAE, incidence tables of severity, action taken, relationship to study drug, outcome and serious AE or not will be presented by center, preferred term and treatment.

The frequency distribution of severity, action taken, relationship to study drug, and outcome of all AE events will be presented by center, and treatment.

6.7.2 *Serious adverse events (SAEs)*

Incidence of serious adverse event will be tabulated. Serious adverse events incidents will be summarized descriptively by center, system organ class/ preferred term, and treatment group.

6.7.3 *Laboratory data*

Descriptive statistics of original data and net changes in hematology and biochemistry data will be presented by center, visit, and treatment.

Results of clinical significance with regard to laboratory data will be summarized with frequency and percentage.

6.7.4 *Physical Examination (PE)*

Incidence table including number and percentage of patient with abnormal PE will be tabulated by center, visit, and treatment for each body system.

The corresponding body system will be analyzed and reported using a transition table. The type of transition includes no change, change to normal, change to non-clinical significance, (NCS), change to clinical significance (CS) for each body system from baseline (Visit 2).

6.7.5 *Vital Signs*

Descriptive statistics of net changes in vital signs including systolic and diastolic blood pressure, heart rate and body temperature will be presented by center, visit, and treatment.

Results of clinical significance with regard to vital sign will be summarized with frequency and percentage.

6.7.6 *ECG*

Frequency table and change in ECG result will be summarized by center, visit and treatment. The transition of ECG is defined as following 4 groups: no change, change to normal, change to non-clinical significance, (NCS), change to clinical significance (CS).

6.7.7 *C-SSRS (Nilsson et al. 2013)*

Results of C-SSRS will be presented by center, visit, and treatment. The baseline of C-SSRS was set at screening visit (Visit 1).

The analysis for C-SSRS will follow the official guidance “Columbia-Suicide Severity Rating Scale - Scoring and Data Analysis Guide.” The 10 categories will be defined according to 10 binary responses (yes/no) on the C-SSRS.

Suicidal ideation is identified if the total score of the five suicidal ideation questions (Categories 1-5) >0 .
Suicidal behavior is identified if the total score of the five suicidal behavior questions (Categories 6-10) >0 .
Suicidal ideation or behavior is identified if the total score of the ten suicidal ideation and behavior questions (Categories 1-10) >0 .

Changes of suicidal ideation, suicidal behavior, and suicidal ideation or behavior from baseline during treatment will be summarized in a shift-table by visit, center and treatment.

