4.1 Inclusion Criteria

1. Aged 18-70 years
2. Female subjects of child-bearing potential must test negative to pregnancy and use appropriate birth control method from the beginning of study to the 15 days later after ending of study
3. Subjects must be able to understand and willing to sign informed consent
4. Able to discontinue the use of any psychotropic medications for the treatment of ADHD symptoms at screening
5. Meet strict operational criteria for adult ADHD according to the Diagnostic and Statistical Manual of Mental Disorders, 5th Edition (DSM-5)
6. A total score of 28 or higher of ADHD Rating Scale-Investigator Rated (ADHD-RS-IV) at screening
7. Have a moderate or severe symptom of ADHD with score of 4 or higher in Clinical Global Impression- Severity (CGI-S) at screening

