7.2 Methods and Timing for Assessing, Recording, and

Analyzing of Safety Parameters

The data obtained before study drug administration in Visit 2 or Visit 1 (if no data at Visit 2) are set as baseline. After the beginning of treatment, the collection of data of safety parameters are performed at planned treatment schedule as [section 5.2](#). AE or SAE will be closely monitored during the study period. CRC shall record these data in CRF in detail. In part II, data are recorded from screening stage to the last visit.

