7.3 Adverse Events (AEs)

Adverse event is any unfavorable and unintended symptom, syndrome, medical condition or experience that develops or worsens within the study period. In this Phase II trial, any clinically significant abnormal findings, including causing the subject to withdraw from the study, requiring treatment or causing apparent clinical manifestations, or judged relevant by the investigator, are considered to be AEs and will be monitored and recorded. AE may not be causal relationship with study medication or clinical study. Whether related to study medication or not, CRC shall record the information of AEs in CRF. The information of AEs contains characteristic, onset and duration, the Investigator's opinion of the relationship to the study drug (unrelated, unlikely, possibly, probably, definitely), outcome (recovered, recovered with residual effects, continuing, death, lost to follow-up), therapy (no action, treatment given, withdrawn from study, temporarily

discontinued) and severity. Common Terminology Criteria for Adverse Events v4.03 (CTCAE [Table 16](#)) is a descriptive terminology and the grading (severity) scale is provided for each AE term.

Table 16. Common Terminology Criteria for Adverse Events

Grade	Description
Grade 1	Mild; asymptomatic or mild symptoms; clinical or diagnostic observations only; intervention not indicated.
Grade 2	Moderate; minimal, local or noninvasive intervention indicated; limiting age-appropriate instrumental activities of daily living (ADL)*.
Grade 3	Severe or medically significant but not immediately life-threatening; hospitalization or prolongation of hospitalization indicated; disabling; limiting self-care ADL†.
Grade 4	Life-threatening consequences; urgent intervention indicated.
Grade 5	Death related to AE.‡

*Instrumental ADL refer to preparing meals, shopping for groceries or clothes, using the telephone, managing money, etc.

†Self-care ADL refer to bathing, dressing and undressing, feeding self, using the toilet, taking medications, and not bedridden.

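### SAP 6.7.1 classifies adverse events by onset date alone, so an event that starts before first dose and worsens on study drug can be left out of the treatment-emergent incidence tables

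*SAP*

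**What the plan says.** SAP 6.7.1 uses two classes. The first is "Pre-treatment AE is the AE onset before the first dosing of study drug". The second is "treatment-emergent AE is the one onset after the first dosing of study drug". It adds: "Pre-treatment AE and treatment emergent AE will be analyzed separately". Neither class mentions a change in severity.

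The detailed output is then tied to the second class. TEAEs are summarised by system organ class and preferred term, and a further set of tables is split by site, term and arm: "For TEAE, incidence tables of severity, action taken, relationship to study drug, outcome and serious AE or not will be presented". Three outputs are not limited to TEAEs: a subject-frequency table of pre-treatment events by center and treatment; an event-level table ("The frequency distribution of severity, action taken, relationship to study drug, and outcome of all AE events will be presented by center, and treatment"); and, in SAP 6.7.2, a summary of serious events by system organ class or preferred term and treatment group.

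Protocol 7.3 defines an adverse event as "any unfavorable and unintended symptom, syndrome, medical condition or experience that develops or worsens within the study period". Protocol 7.2 adds: "In part II, data are recorded from screening stage to the last visit". The schedules in protocol Table 15 and SAP 5.2.3, however, mark AE/SAE evaluation only from Visit 2.

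**The concern.** Events between consent and first dose are foreseeable here. Inclusion criterion 4 requires subjects to be "Able to discontinue the use of any psychotropic medications for the treatment of ADHD symptoms at screening". Protocol 5.2.1 uses the screening phase as a washout, and protocol 5.3 has some subjects stop hypnotics for a week before starting. The SAP itself plans a table of pre-treatment events.

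A mild complaint that starts in that window and becomes moderate or severe on study drug is information the arm-by-arm safety tables should carry. Under an onset-only rule it keeps its pre-dose date and stays out of the tables that compare arms by preferred term. SAP 5.4 drops the between-arm tests after termination, so the descriptive safety tables are a main remaining output of the trial.

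**Working it through.** No stated figure is in dispute, so the check is mainly a comparison of texts.

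1. **Definition of an event (protocol 7.3).** Onset or worsening, at any time in the study period.
2. **Definition of a TEAE (SAP 6.7.1).** Onset after first dose. There is no worsening limb. SAP 5.4 states that the analysis follows the protocol and lists no change to event handling, so the omission is not explained.
3. **Is worsening captured another way?** Protocol 7.3 lists the items recorded for each event, including onset, duration, severity, outcome and therapy. It lists no date or grade for a worsening. Neither document tells sites to open a new record when an event worsens.
4. **Following one event through the tables.** Take a grade 1 event that starts between Visit 1 and Visit 2, is entered once, and reaches grade 3 in week 3.

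| Output | Is the event included? | Does it show on-drug worsening by preferred term and arm? |
|---|---|---|
| TEAE by system organ class and preferred term | No | No |
| TEAE severity, action, relationship, outcome and seriousness by preferred term | No | No |
| Pre-treatment event table | Yes | No: it counts the event as pre-treatment |
| Distribution over all events | Yes | No: not described as split by preferred term, and it pools pre-dose with on-drug events |
| Serious events (SAP 6.7.2) | Only if serious | No: it shows term and arm, but not that a pre-dose event worsened |
| Protocol 8.3 summary of all adverse events | Yes | No: it shows term and severity, but does not separate pre-dose from on-drug events |

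5. **Size per subject.** Protocol 8.1 gives 23 subjects per arm at stage 1 (3 × 23 = 69). One subject whose only on-drug event is of this kind changes an arm's overall TEAE incidence by 1/23 = 0.043, or 4.3 percentage points. SAP 6.7.1 counts a subject once per preferred term, so a single preferred-term row moves by the same 4.3 points if the subject has no other TEAE under that term. A subject who already has another TEAE leaves the overall incidence unchanged.
6. **Number of subjects.** The documents give no rate of pre-treatment events and no rate of worsening, so an expected count cannot be derived.

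Changing the TEAE definition alters no sample-size or efficacy figure.

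**The case against.** The strongest reply is that the documents are silent rather than wrong. If worsening is itself an adverse event under protocol 7.3, its onset is the time of worsening; when that falls after first dose, the SAP's rule already makes it a TEAE. This reading is open, and a site that entered worsenings as new records would produce the right result. But nothing requires sites to do so. The classification then depends on site habit, which the SAP should not leave open.

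A reader might infer that the SAP contradicts the protocol. It does not: protocol 7.3 defines an adverse event, and the protocol has no TEAE definition to contradict. A reader might also infer that such events disappear from the safety report. They do not: they remain in the pre-treatment table, the all-event distribution, the protocol's all-event summary and, if serious, the serious-event summary. Protocol 8.4 also lists premature terminations with dates and reasons.

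Two further points stand. The exposed set is narrow: it holds only events that start and are recorded in a screening phase of at most about two weeks, and then worsen on drug. The direction of bias is not settled either. Worsening caused by the drug would arise in the active arms, and leaving it out would understate harm. Worsening caused by stopping earlier medication would be expected in all three randomised arms, placebo included.

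**Conclusion.** The point holds as a gap in the TEAE definition. Applied as written, and with one record per event, SAP 6.7.1 leaves an event that starts before first dose and worsens on study drug out of the TEAE incidence tables. The remaining outputs keep the event but do not show its aggravation by preferred term and arm.

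The effect is 4.3 percentage points of an arm's TEAE incidence per affected subject. This assumes 23 analysed subjects in the arm and no other TEAE in that subject. The figure for 33 per arm (1/33 = 3.0 points) does not arise, because SAP 5.4 records termination after the interim analysis. Any total over subjects would rest on rates the documents do not give. The point deserves correction because the tables affected are the main safety comparison and the change is small.

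**What to change.** In SAP 6.7.1, define a TEAE as an adverse event with onset on or after first dose, or one with onset before first dose that increases in grade, becomes serious or leads to withdrawal after first dose.

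The SAP (dated April 25, 2024) already records termination, so a new entry instruction to sites would come too late. Apply the definition instead by reviewing every pre-treatment event still ongoing at first dose, using the recorded severity, seriousness and action taken. Query the site where the record does not show whether or when the grade changed, since protocol 7.3 does not list that date among the items collected.

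Also reconcile protocol 7.2, which has data recorded from screening, with protocol Table 15 and SAP 5.2.3, which start AE/SAE evaluation at Visit 2. That difference decides which washout events are in the database at all.

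The cost is one sentence in the SAP, a short data review with possible queries, and slightly higher TEAE counts.

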5.2.2 Part II.- Treatment Period (Visit 2~6)

Subjects who meet the eligibility criteria will be enrolled and take study drugs. At visits 2 to 5, each subject will be dispensed a supply of study drug sufficient for next 2-week treatment period. The subjects will be instructed to take one dose (i.e., two capsules) after a meal thrice daily. Drug compliance is important for the safety and efficacy evaluations. Study coordinator needs to make sure drug adherence of the subjects is at least

80% during the treatment period. Otherwise, study coordinator(s) must report a protocol deviation including lower than 80% compliance and over 100% compliance during the treatment period. At visits 2, 3, 4, 5 and 6, the safety and efficacy parameters will be evaluated by the following items. Baseline data will be collected before dosing study drug.

- Physical examination: skin, head, neck, eyes, ears, nose, throat, heart, lungs, abdomen (liver, spleen), neurological examination, lymph node and extremities.
- Vital sign: heart rate, blood pressure, body temperature
- ECG (Only at visit 6)
- Hematology: RBC, WBC, platelets, hematocrit, hemoglobin, prothrombin time (PT), partial thromboplastin time (aPTT). (Only at visit 2, 4 and 6)
- Blood chemistry: AST, ALT, LDH, total bilirubin, BUN, serum creatinine, free thyroxine (FT4), TSH, sodium, calcium, potassium, LDL, HDL, triglyceride, cholesterol. (Only at visit 2, 4 and 6)
- CAARS-S:S, CGI- -S (only for Visit 2), CGI- I (only for Visit 3 – 6), ADHD-RS-IV, E-SCT, C-SSRS and concomitant medication evaluation.
- AE/SAE evaluation
- Drug accountability

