7.1 Specification of Safety Parameters

Safety parameters are outlined as follows:

- Data collected from the physical examinations, vital sign, ECG and laboratory test in scheduled visit
- Adverse events reported
- Serious adverse events reported
- C-SSRS evaluation

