6.4 Baseline Determined

The data obtained before study drug administration in Visit 2 or Visit 1 (if no data at Visit 2) are set as baseline. For all other endpoint measurements, the last non-missing values before the first IP administration will be used as the baseline for the respective endpoints.

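### SAP 6.7.7 fixes the C-SSRS baseline at screening, against protocol 7.2 and SAP 6.4, so shifts are misclassified for any subject whose status changes before the first dose

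*SAP*

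**What the plan says.** SAP 6.7.7 sets the baseline for this scale in one sentence, with no condition and no reason: "The baseline of C-SSRS was set at screening visit (Visit 1"). The same section then builds its summary on that baseline: "Changes of suicidal ideation, suicidal behavior, and suicidal ideation or behavior from baseline during treatment will be summarized in a shift-table", broken down by visit, center and treatment.

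Two other places give a different rule.

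- Protocol 7.1 lists "C-SSRS evaluation" among the safety parameters. Protocol 7.2 sets the baseline for those parameters: "The data obtained before study drug administration in Visit 2 or Visit 1 (if no data at Visit 2) are set as baseline".
- SAP 6.4 repeats the protocol's sentence. For all remaining endpoints it adds that "the last non-missing values before the first IP administration will be used as the baseline for the respective endpoints".

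A Visit 2 value should normally exist. C-SSRS is ticked at every visit from 1 to 7 in protocol Table 15 and in SAP 5.2.3. Protocol 5.2.2 includes it in the items for Visits 2 to 6 ("E-SCT, C-SSRS and concomitant medication evaluation") and adds: "Baseline data will be collected before dosing study drug".

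SAP 5.4 says the analysis follows the protocol. The one change it lists is that the between-arm tests are dropped after the trial was terminated.

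**The concern.** A shift table is only as good as its starting point. Up to two weeks separate Visit 1 from Visit 2. Protocol 5.2.1 describes that interval as partly a washout, and inclusion criterion 4 requires subjects to be able to stop psychotropic medication for ADHD. A subject's C-SSRS status can change in that window for reasons unrelated to study drug. With the baseline before the window, such changes are carried into comparisons that are labelled as change during treatment.

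Suicidal ideation and behavior by C-SSRS is a named safety endpoint in the protocol synopsis and in SAP 5.3.2. With the between-arm tests dropped, the descriptive tables are what a reader will use to judge it.

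**Working it through.** The plan gives no figure to reproduce. The check compares the rules and then lists what each does to the shift table.

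**Step 1: which visit each rule selects when both assessments exist**

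| Source | Baseline for C-SSRS |
|---|---|
| Protocol 7.2 (safety parameters) | Visit 2, pre-dose |
| SAP 6.4, first sentence | Visit 2, pre-dose |
| SAP 6.4, second sentence | Visit 2, as the latest pre-dose value |
| SAP 6.7.7 | Visit 1 |

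SAP 6.7.7 stands alone. The rules agree only when the Visit 2 assessment is missing.

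**Step 2: effect on the shift at a post-dose visit**

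Code status as 1 (ideation or behavior present) or 0 (absent) at Visit 1, at Visit 2 pre-dose and at one post-dose visit. That gives 2 × 2 × 2 = 8 patterns.

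| Visit 1, Visit 2, post-dose | Visit 1 baseline (SAP 6.7.7) | Visit 2 baseline (protocol 7.2) |
|---|---|---|
| 0, 0, 0 | no change | no change |
| 0, 0, 1 | new onset | new onset |
| 1, 1, 0 | improvement | improvement |
| 1, 1, 1 | no change | no change |
| 0, 1, 1 | new onset | no change |
| 1, 0, 1 | no change | new onset |
| 0, 1, 0 | no change | improvement |
| 1, 0, 0 | improvement | no change |

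The four patterns in which Visits 1 and 2 agree are unaffected. The four in which they differ are all classified differently. The error runs both ways: pattern 0, 1, 1 creates a false on-treatment onset, and pattern 1, 0, 1 conceals a real one.

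**Step 3: is there a Visit 2 row?**

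The SAP does not say. The protocol's heading for section 5.2.2 is "Treatment Period (Visit 2~6"), and both schedules place Visit 2 under treatment. A by-visit table of changes during treatment could therefore include it. If it does, any subject with 0 at Visit 1 and 1 at Visit 2 appears as shifted before taking any drug. If the table starts at Visit 3, this extra effect disappears, but every reclassification in Step 2 remains.

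**Step 4: consistency with the adverse event tables**

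SAP 6.7.1 separates pre-treatment from treatment-emergent events at the first dose. A pre-dose episode that is also recorded as an adverse event could therefore be pre-treatment in one table and a change from baseline in the other.

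**Step 5: size**

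The documents give no rate of change in C-SSRS status between Visits 1 and 2, so the number of subjects affected cannot be calculated. For scale only: at the planned stage I size of 23 per arm, one misclassified subject is 1/23 = 4.3% of an arm.

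**The case against.** The best defence is that a specific rule overrides a general one, so SAP 6.7.7 may be a deliberate exception to SAP 6.4. That would settle the conflict inside the SAP, but not the conflict with protocol 7.2. The exception is neither explained nor listed in SAP 5.4. Section 6.7.7 says it follows a published C-SSRS scoring guide, but does not attribute the choice of Visit 1 to it.

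Several points in the plan's favor stand.

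- A reader might infer that pre-dose suicidality at Visit 2 is certain to be reported as an on-treatment change. The documents do not establish this. No Visit 2 row is specified, and the SAP's section on concomitant medications starts the treatment duration at the first dose.
- The little evidence on frequency points low. Phase I scores were all zero (protocol 1.3.1), Part I reported no increased risk (1.3.2), and exclusion criterion 8 removes subjects judged to be at current risk.
- SAP 6.7.7 also presents C-SSRS results by visit, so a careful reader could see Visit 2 status separately.
- Changes before dosing cannot be caused by the assigned drug, so disagreement between Visits 1 and 2 is balanced across arms in expectation. This helps only in part. Expectation says little about a handful of subjects, and what happens after dosing within that group can depend on the arm.

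None of this removes the contradiction or the four reclassified patterns.

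**Conclusion.** The contradiction is explicit, and the rule as written gives wrong shifts by the protocol's own definition of baseline. The conclusion assumes that the protocol's definition governs, that the Visit 2 assessment is made before dosing as protocol 5.2.2 requires, and that at least one subject changes status between the two visits. If nobody does, the two tables are identical.

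The size is unknown, and the reach is limited to a descriptive safety table with no test attached. The primary endpoint is not affected.

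Two stronger readings should be resisted. One is to attach a count or percentage of misclassified subjects, which nothing in the documents supports. The planned maximum of 99 is not a usable denominator either, because SAP 5.4 reports termination at the interim. The other is to argue from the recall period of the Visit 1 form or from a class risk of norepinephrine reuptake inhibitors; the documents state neither.

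**What to change.** Replace the baseline sentence in SAP 6.7.7 with: *Baseline is the last non-missing C-SSRS before the first dose (Visit 2; Visit 1 only if Visit 2 is missing).* Start the on-treatment shift table at Visit 3, and show Visit 1 and Visit 2 as pre-treatment results so that changes during screening stay visible.

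If the sponsor does want a screening baseline, SAP 5.4 should declare it as a departure from protocol 7.2 with a reason, and both versions of the table should be shown.

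The cost is one SAP sentence and a rerun of one table, with no new data. Because the change restores the rule already in the protocol, it adds no new analysis choice after the interim results.
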